**Gingival crevicular fluid characterization during orthodontic treatment**

**[name]**

**Associate Professor**

**Department of Orthodontics, College of Dentistry,**

**University of Illinois at Chicago**

**V3; 6/22/2017-Recent IRB approval 10/3/2018-10/2/2021**

## Gingival crevicular fluid and orthodontic treatment

During Orthodontic tooth movement, teeth are moved through alveolar bone under applied forces. The applied mechanical loading force must be transferred to the alveolar bone via periodontal ligament (PDL) [1]. This process of mechanotransduction stimulates bone remodeling during which osteoblasts produce bone on the tension side and osteoclasts resorb bone on the compression side of the PDL [2-6]. Complex interactions between osteoblasts and osteoclasts involve numerous biologic molecules including cytokines and growth factors [7]. During the tooth movement, the expression of cytokines such as interleukin (IL)-1 $\beta$ , IL-6, IL-8, prostaglandin E2, RANKL and MMP1 in PDL will be up-regulated [8-10]. The sequence of events from the mechanotransduction commanding the tightly controlled accomplishment of osteogenesis at tension sides and osteoclastogenesis at compressive sides is not completely understood [11, 12].

The gingival crevicular fluid (GCF) is a transudate of interstitial tissues which is produced by an osmotic gradient [13] and it is released into the crevicular crevices at a flow rate of about 3  $\mu$ l/h [14]. Orthodontic treatment is triggered by an inflammatory process and it has been hypothesized that the quantification of specific biomarker within the GCF can be determined using Periotron [15]. However contrasting results have been reported in the literature, which studies showing both increased or unchanged GCF volumes incident to orthodontic treatment.

Given that the orthodontic treatment is triggered by a set of inflammatory cytokines which are released into the crevicular fluid during the mechanical loading, and its homeostasis is dependent on mechanical stimulation. An understanding of the biological response of crevicular fluid to mechanical loading could further advance the knowledge of orthodontic treatment.

In this study, we will investigate the biological response of gingival crevicular fluid before and after the initial wire placement of orthodontic treatment to determine the differentially expressed genes and proteins related to mechanotransduction.

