## Materials and Methods

### *Eligibility criteria for the collection of gingival crevicular fluid*

One Hundred Healthy, non-smoking patients aged 11-35 years old who require orthodontic treatment with first premolar extraction at the orthodontic clinic at College of Dentistry, University of Illinois at Chicago (UIC) will be included. The informed consent will be presented to patients and parent(s) [legal guardian(s)] and signed before the procedure. The patient will be screened for the inclusion criteria at time of consent. The written assent will also be obtained from minor subjects. Before the treatment, periapical radiographs will be taken on both maxillary canines to verify the root length and morphology so the pre-fabricated power arms on the canine brackets will be closed to center of resistance of the canines. Fixed orthodontic appliances (0.018-in; MBT prescription) will be placed in the subject with an auxiliary vertical slot in the maxillary canine brackets (Dentsply International, York, NY) to accommodate the prefabricated power arms. The subjects will be referred for extraction of the maxillary first premolars. A temporary anchorage device will be placed between maxillary second premolar and maxillary first molar, 5 mm from alveolar crest for anchorage and reference purposes. The teeth in maxillary arch will be leveled and aligned before canine retraction. Once

0.016x0.016 stainless steel archwires (Dentsply International) are placed, the canine retraction will be achieved using calibrated 70-g [127] nickel-titanium closing-coil springs (Dentsply International) connected from a temporary anchorage device to the power arm on the canine brackets that allowed application of the force closer to the center of resistance of the tooth.

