#### *Collection of gingival crevicular fluid*

Patients will be seated in the dental chair in an upright position. The selected site will be air-dried and isolated with cotton rolls. Without touching the marginal gingiva, supragingival plaque will be removed to avoid contamination of the paper strips. The absorbent paper strips will be placed gently in the sulcus and the absorbed paper strips will be pooled and placed in a sterile eppendorf tube containing 200 ul of phosphate buffer saline. The collected sample will be coded with unique ID numbers and kept at -80C until analyzed. The key for the IDs will be kept in a locked cabinet in Rm#237B , College of Dentistry. The patient will be informed not to take NSAIDs but paracetamol after the orthodontic treatment. The collection of GCF will be performed before bracket placement, before canine retraction, 2 weeks after canine retraction, 5 weeks after canine retraction and 7 weeks after canine retraction.

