#### *Intraoral scanning*

The patients' occlusion and jaws will be scanned using an intraoral digital scanner. The intraoral scanning will be performed at the highest resolution at each studied timepoint. The scanning data will be exported as stereolithography binary file format (.stl) and imported to a sophisticated processing software package (Geomagic® Control 14, Geomagic®, Research Triangle Park, NC, USA). The miniscrews and palatal rugae structure will be used as reference points

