#### *ELISA*

The GCF samples will first be homogenized for 30 s and centrifuged for 5 min at 1500 g to elute. The elute will then used as sample for ELISA estimation from GCF samples. The GCF sample will be detected IL1, IL6, IL8, OPG and RANKL. The ration of OPG and RANKL will be calculated and determine the potential of PDL to activate osteoclasts.

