#### *microRNA analysis*

Total RNA will be extracted from the stored GCF samples using miRNeasy serum/plasma kit (Qiagen, Valencia, CA). Quantity of the total RNA will be determined by NanoDrop spectrophotometer (Thermoscientific). The total RNA will be subjected to quantitative realtime RT-PCR using Taqman® microRNA RT-PCR assays specific to hsa-miR-21, -29a, b and c. hsa-let-7d, g and i will be used as an internal control [112, 129]. The samples from each subject will be analyzed using a 7900HT realtime PCR system (Applied Biosystems).

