### **Statistical Analysis**

All the analyses will be performed in triplicate for three independent experiments to confirm reproducibility of the results. Quantitative data will be presented as means  $\pm$  SD from three independent experiments. Wilcoxon Sign-ranked analysis will be used to determine the mean difference before and after treatment at  $P = 0.05$ .

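### Five crevicular-fluid samples per patient are analysed only by a paired before/after test, so no planned analysis uses them jointly or tests change across weeks 2, 5 and 7

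*Combined protocol and SAP*

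**What the plan says.** The section on collecting gingival crevicular fluid schedules samples "before bracket placement, before canine retraction, 2 weeks after canine retraction, 5 weeks after canine retraction and 7 weeks after canine retraction". That is two samples before retraction and three during it. Enrolment is "One Hundred Healthy, non-smoking patients aged 11-35 years old". The markers are five proteins ("The GCF sample will be detected IL1, IL6, IL8, OPG and RANKL"), the OPG/RANKL ratio, and four microRNAs ("assays specific to hsa-miR-21, -29a, b and c").

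The Statistical Analysis section has three sentences, and only the last is inferential: "Wilcoxon Sign-ranked analysis will be used to determine the mean difference before and after treatment", at a 0.05 level. Neither the before nor the after side is tied to a visit. The introduction states the aim as a comparison "before and after the initial wire placement of orthodontic treatment", whereas three of the five samples are timed from canine retraction. No repeated-measures model, overall visit test, multiplicity rule or missing-data rule is given.

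**The concern.** A signed-rank test takes one difference per patient. However many such tests are run, each ignores three of the five samples and omits any patient who lacks either value of its pair. The reason to sample at "2 weeks after canine retraction, 5 weeks after canine retraction and 7 weeks after canine retraction" is to see how the response develops, and no planned analysis asks whether a marker differs between those weeks.

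Two things are at stake. If the response is brief, the result depends on which week happens to be tested. If it is sustained, the study gives up precision that it could have from samples already collected.

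**Working it through.** **Inputs from the document.** 100 patients; five samples each; paired signed-rank test; level 0.05. No power, effect size, SD, within-patient correlation or dropout rate is given, so there is no planned figure to reproduce.

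**Assumptions.** Two-sided 5%; log-scale SD 1 at each visit; equal correlation ρ = 0.3 / 0.5 / 0.7 between visits; reference = the sample just before retraction; complete data except in step 1. Simulated figures carry an error of one to three percentage points.

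**1. Use of the samples.** Each test uses 2 of 5 samples. If a fraction m of samples is missing independently, complete pairs are (1 − m)²: 0.95² = 90%, 0.9² = 81%, 0.8² = 64%.

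**2. One pair tested (ρ = 0.5, simulation).**
- Response of 0.3 SD at week 2 only: 83% power if week 2 is the after visit, about 5% if it is week 5 or week 7.
- Response fading 0.4, 0.2, 0 SD over weeks 2, 5 and 7: 97% with the week-2 pair, 5% with the week-7 pair.

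**3. Each retraction week tested against the reference.** Unadjusted, three independent tests would give 1 − 0.95³ = 14.3% false positives. Sharing the reference makes the tests correlated, and simulation at ρ = 0.5 gives about 12-13% per marker. Adjusted to 0.05/3 each, the familywise rate is about 5%, with the power shown in step 4.

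**4. Joint 3-df test.** The three differences from the reference have covariance (1 − ρ)(I + J), with J the matrix of ones and inverse (I − J/4)/(1 − ρ).
- Week-2-only 0.3 SD, ρ = 0.5: noncentrality 100 × 0.09 × 0.75 / 0.5 = 13.5. The noncentral F on 3 and 97 df gives 87%.
- Constant 0.2 SD: noncentrality 100 × 0.04 × 0.75 / (1 − ρ) = 4.29 / 6 / 10, giving 37 / 50 / 74%.

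| Response | Three tests at 0.05/3 | Joint test (simulated) |
|---|---|---|
| Week 2 only, 0.3 SD, ρ = 0.5 | about 68% (71% in another run) | 88% |
| Fading 0.4, 0.2, 0 SD, ρ = 0.5 | 93% | 98% |
| Constant 0.2 SD, ρ = 0.3 / 0.5 / 0.7 | 43 / 55 / 78% | 37 / 49 / 74% |

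**5. Averaging the three retraction weeks.**
- Variance of one paired difference: 2(1 − ρ).
- Variance of the three-week mean minus the reference: (1 + 2ρ)/3 + 1 − 2ρ = (4/3)(1 − ρ).
- Ratio: (4/3)/2 = 0.667, equivalent to 100/0.667 = 150 patients on one pair.

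Power for a constant 0.2 SD, with Φ the normal distribution function and 0.955 the signed-rank efficiency under normality:
- One pair: Φ(0.2·√95.5 / √(2(1 − ρ)) − 1.96) = Φ(−0.31), Φ(−0.01), Φ(0.56) = 38 / 50 / 71%. Simulated: 37 / 49 / 69%.
- Mean of three, model contrast: Φ(0.2·√100 / √((4/3)(1 − ρ)) − 1.96) = Φ(0.11), Φ(0.49), Φ(1.20) = 54 / 69 / 89%. Simulated: 54 / 69 / 87%.
- Mean of three by signed-rank, with √95.5 in place of √100: 53 / 67 / 87%. So nearly all the gain comes from averaging, not from the change of test.

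**6. Where averaging does not help.** For the week-2-only 0.3 SD response (ρ = 0.5), the signed-rank test on the three-week mean has 23% power. If correlation decays with the gap between visits (r₀·exp(−decay × gap), r₀ 0.5-0.9, decay 0.02-0.2 per week), the variance ratio is 0.55-0.68 against a week-5 or week-7 pair but 0.71-1.17 against a week-2 pair.

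**The case against.** The strongest reply is that the plan never confines itself to one pair. A reader might infer from the wording that most retraction samples will go unused and that some weeks will go untested. The text does not say so, and it does not exclude a signed-rank test at each visit. On that reading every retraction sample enters some test and no week is missed. With Bonferroni adjustment those tests slightly outperform the joint test for a constant response and come close to it for a graded one. This stands. What it does not supply is any test of change between weeks 2, 5 and 7, any rule for adjustment, or any use of patients outside their complete pairs.

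A reader might also set 5% against 98% power and take that as the expected loss. It arises only if the response fades and the wrong week is tested; the week-2 pair has 97% in the same scenario.

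Nor is every single pair the poorer analysis. A week-2 pair can be as precise as the average, or more so, when correlation decays with time.

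Lastly, omitting patients with a missing value is a property of the test and not a rule the plan states. Its size cannot be known from the document.

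**Conclusion.** The concern holds in a limited form. Five samples are collected, the one named test compares two, and no analysis uses the series jointly or tests change during retraction. That much is plain from the text. The planned test is valid, so this is an improvement that should be made, not a fatal fault.

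The size of the loss depends on how the unstated details are settled:
- One pair: a response limited to another week is found at about the 5% error rate.
- Three unadjusted visit tests: about 12-13% false positives per marker at correlation 0.5.
- Three adjusted visit tests: about 20 points less power than a joint test for a brief week-2 response (68% against 88%), and slightly more for a constant one.
- Sustained response: the gain belongs to the three-week average (54 / 69 / 87% against 37 / 49 / 69% for one pair). The joint test, at 37 / 49 / 74%, barely improves on a single pair.

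All of these figures rest on assumed SDs, effects, correlations and missing rates, since the document gives none, and most assume equal correlation between visits.

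**What to change.** Replace the test sentence in the Statistical Analysis section with the following plan for each marker.

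- Take one log-scale value per patient per visit and fit a repeated-measures model with visit as a five-level factor, using every available sample.
- Use either an unstructured within-patient covariance with no random patient effect, or a random patient intercept with patient-clustered standard errors. A random patient effect on top of an unstructured covariance is over-parameterised.
- Name the reference sample and pre-specify one test of response against it: the mean of weeks 2, 5 and 7 if a sustained response is expected, or the joint 3-df test if the time course is the question.
- Report each visit's ratio of geometric means to the reference with a 95% CI, and a test of change across weeks 2, 5 and 7.
- Keep the signed-rank test on each patient's mean log value over weeks 2, 5 and 7 minus the reference, as a distribution-free check of the mean contrast only. It cannot confirm a joint-test result for a brief response.

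The cost is SAP wording and a little more analysis work, with no new patients, visits or assays. The drawback is reliance on a log-scale model.
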